In our pilot study of 91 community-dwelling postmenopausal women of European ancestry treated with 2300-2500 IU of vitamin D₃ daily for 4-6 months, we utilized novel liquid chromatography, tandem mass spectroscopy (LC-MS/MS) methodology to evaluate serum levels of cholecalciferol (vitamin D₃) and 24,25(OH)₂D at baseline and after 4-6 months. We observed the anticipated relationship with cholecalciferol: a greater increase in circulating vitamin D₃ is associated with a greater increment in 25(OH)D. Additionally, we reproduced the observation of others [Wagner et al., 2011] that a higher ratio of 24,25(OH)₂D/25(OH)D after supplementation is associated with a less robust increase in 25(OH)D. Thus, our pilot work supports the premise that smaller increments in 25(OH)D may result from relatively low vitamin D₃ input (presumably from poor absorption) and/or greater degradation. To this end, we performed multiple regression analysis to determine the characteristics that might enable prediction of the 25(OH)D achieved with supplementation. The equation from the final model was: post-treatment 25(OH)D = 8.3 + (1.05*baseline 25(OH)D) – (7.7*baseline 24,25(OH)₂D) + (0.53*follow-up cholecalciferol) + (4.2*follow-up 24,25(OH)₂D). This model had an adjusted $R^2 = 0.55$ with $p < 0.001$ for all the parameters, thus accounting for approximately half of the variance in the final 25(OH)D level. The baseline values of cholecalciferol could not be used in this model because the data were highly skewed (virtually all values were zero since the assay is currently not capable of measuring very low concentrations of cholecalciferol). Nonetheless, these preliminary data support the dosing algorithm described below.

HYPOTHESES AND SPECIFIC AIMS

Aim 1:

Determine the efficacy of our dosing algorithm in achieving total 25(OH)D concentrations of 35-50 ng/mL in women of European and African ancestry.

To validate our vitamin D₃ dosing algorithm, we will conduct a randomized, double-blind, controlled, six-month duration clinical trial of daily oral vitamin D₃ to determine the efficacy of dosing following our algorithm compared to 2500 IU/day (control arm) in achieving the target total 25(OH)D concentration of 35-50 ng/mL. Participants will be community-dwelling post-menopausal women of European and African ancestry, who have a baseline total serum 25(OH)D of ≥ 10 but < 30 ng/mL.

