H1a: The percent of individuals with total 25(OH)D of 35-50 ng/mL will be significantly higher in the dosing algorithm arm than in the control arm.

H1b (exploratory aim): The percent of African ancestry women with total 25(OH)D of 35-50 ng/mL will be similar to (i.e., not significantly different than) that in women of European ancestry.

Aim 2:

Determine additional factors that predict response to vitamin D supplementation.

We will expand our predictive model to include baseline serum cholecalciferol and body composition, measured by dual-energy x-ray absorptiometry (DXA), and genotypes in the *GC* and *CYP2R1* genes. In exploratory analyses we will also determine the effect of self-reported ancestry on our dosing algorithm.

H2a: Baseline body mass, but not total body fat, will be negatively associated with total 25(OH)D after supplementation, indicating that individuals with larger body size, not just body fat, will require a higher dose of vitamin D₃ to attain the target total 25(OH)D range.

H2b: Baseline cholecalciferol will be positively associated with 25(OH)D after supplementation, where individuals with higher values will require a lower dose.

H2c: There will be a negative association between the number of risk alleles in the two genes and total 25(OH)D after supplementation, where individuals with more risk alleles will require a higher dose.

Completion of these aims will allow us to validate and refine our vitamin D dosing algorithm. This predictive tool will allow clinical estimation of the dose needed to achieve a target 25(OH)D level, advancing clinical care by allowing personalization of vitamin D supplementation. Moreover, the insight gained from the proposed study will enable clinical trials of other vitamin D-related outcomes to achieve more effective vitamin D supplementation by using our dosing algorithm. This will enhance future research proposals by radically improving the study design.

STUDY DESIGN

Study Design and Population.

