The proposed study is a randomized, double-blind, controlled, multi-center clinical trial of six months of daily oral vitamin D₃ (cholecalciferol). This study will randomize 334 community-dwelling post-menopausal women of European and African ancestry (~167 from each ancestry) in a 1:1 ratio between the control arm and the dosing algorithm arm using stratified block randomization with a block size of six and stratification by site (ancestry). The sample size of 334 includes 10% over-recruitment to allow for loss to follow-up. The proposed study will focus on post-menopausal women because this is the subset of the population that both [name] and [name] preliminary data are drawn from. Moreover, 25(OH)D concentrations are typically lower in women and in older individuals, since production of vitamin D in the skin following sun exposure decreases with age. Therefore, this group of individuals is likely to benefit the most from vitamin D supplementation, especially when personalized based on biology using our dosing algorithm.

Vitamin D Preparation and Dosing.

All vitamin D₃ preparations will be produced by Tishcon Corp (Westbury, NY). Vitamin D₃ content of these preparations will be independently validated in the laboratory of [name] prior to study initiation and annually thereafter to assure stability. The control group will receive 2500 IU of vitamin D₃ daily while the dosing algorithm group will initially receive 1000, 2500, or 4000 IU daily. The rationale for these dosing arms is based on our pilot data. First, we aim to reduce the variation in achieved 25(OH)D following vitamin D supplementation, bringing more individuals into the target range of 35-50 ng/mL. In our pilot study, participants received 2300-2500 IU/day, a dose similar to many other vitamin D supplementation trials. Therefore, to test the alternate hypothesis that our dosing algorithm will improve vitamin D supplementation beyond that typically given in clinical trials, the appropriate control group should receive 2500 IU/day. Second, in our multiple regression analysis to determine characteristics that predict 25(OH)D achieved after supplementation, the following equation had an adjusted R^2 of 0.55 ($p < 0.001$): post-treatment 25(OH)D = 8.3 + (1.05*baseline 25(OH)D) –

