$(7.7 \times \text{baseline } 24,25(\text{OH})_2\text{D}) + (0.53 \times \text{follow-up cholecalciferol}) + (4.2 \times \text{follow-up } 24,25(\text{OH})_2\text{D})$. Using only the baseline values, which would be available at an initial clinical visit, including baseline cholecalciferol, $\text{post-treatment } 25(\text{OH})\text{D} = 18.19385 + (0.65967 \times \text{baseline } 25(\text{OH})\text{D}) + (1.02393 \times \text{baseline } 24,25(\text{OH})_2\text{D}) + (0.13564 \times \text{baseline cholecalciferol})$. For the current study, the dosing at both baseline and the 3-month follow-up visit will be determined using this equation to predict post-treatment 25(OH)D (at the 3-month follow-up visit, the 3-month values will be substituted for the baseline values in the equation). Specifically, for those whose predicted 25(OH)D is ≥ 35 ng/mL and < 50 ng/mL, we will administer a dose of 2500 IU daily. For those whose predicted 25(OH)D is < 35 ng/mL, we will administer 4000 IU/day and for those whose predicted 25(OH)D is > 50 ng/mL we will administer 1000 IU/day. The target 25(OH)D range was selected as nearly all experts agree that 25(OH)D levels above ~ 30 - 32 ng/mL are adequate; hence we have chosen a target level ≥ 35 ng/mL to account for assay variability, thereby assuring that all have concentrations > 30 - 32 ng/mL. An upper limit of 50 ng/mL was selected based on evidence suggesting that 25(OH)D levels above this value might have adverse effects [Sempos et al., 2013; Stolzenberg-Solomon et al., 2010]. All three of the daily doses are within the range considered to be safe by a recent Institute of Medicine report [Ross 2011].

INCLUSION/EXCLUSION CRITERIA

Inclusion criteria:

- Healthy, community-dwelling postmenopausal woman (natural menopause, 12 consecutive months without menstruation, or surgical menopause and \geq age 55, or surgical menopause and postmenopausal symptoms \geq 12 months ago)
- Self-reported $> 50\%$ European or $> 50\%$ African ancestry
- Able and willing to sign informed consent as affirmed by research staff person obtaining consent
- Screening serum 25(OH)D concentration of 10.0-29.9 ng/mL
- Willing to not alter the amount of their baseline vitamin D supplementation during the course of this study
- Willing to use sunscreen (SPF ≥ 15) when sun exposure of > 15 minutes is expected during the months of May through September

Exclusion criteria:

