In the primary analyses for Aim 1 (H1a), treatment group (control versus dosing algorithm) will be the independent variable; for H1b, ancestral group (European versus African ancestry) will be the independent variable and only individuals in the dosing algorithm group will be included. For both H1a and H1b, the dependent variable will be the percent of individuals with a 25(OH)D concentration of 35-50 ng/mL at the three- and six-month follow-up visits. A two-sample test for binomial proportions will be used. We will also determine the effect of treatment group and ancestry on free (bioavailable) 25(OH)D concentration using an analysis of variance.

The control group will be used as an unbiased external validation of our dosing algorithm, in which we will repeat the multiple regression analysis in the control sample and compare the coefficients to those in our original equation. In Aim 2 (H2a-c), we will further develop our dosing algorithm by determining if baseline serum cholecalciferol, baseline body composition, and genotypes in the *GC* and *CYP2R1* genes are associated with response to vitamin D₃ supplementation. In exploratory analyses we will include two-way interaction terms between ancestry and each of our primary predictors to determine if the effect of any of these biologic predictors varies by ancestral group.

Sample Size Justification.

For H1a, the outcome variable will be the percent of individuals with a 25(OH)D concentration of 35-50 ng/mL at the three- and six-month visits. Based on our preliminary data, we expect 40% of the individuals receiving 2500 IU/day to achieve 25(OH)D of 35-50 ng/mL. We expect our dosing algorithm to increase this to at least 55%, a conservative estimate. We calculated the sample size required in each arm to detect this difference with power of 80% and a one-sided significance level (α) of 0.05. A sample of 167 participants in each arm, decremented to 150 by a 10% loss to follow-up will be required.

In the multiple regression models for H2a-c, with a total sample size of 150 from the control arm, an α of 0.05, and power of 80% we would be able to detect a factor that accounts for as little as 8% of the variation in 25(OH)D concentration after vitamin D supplementation.

Multisite Conduct Plan

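### The control-arm external validation compares refitted coefficients with an unnamed equation and does not measure how accurately the dosing equation predicts 25(OH)D in individual women

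*Combined protocol and SAP*

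**What the plan says.** The Statistical Methods section gives the control arm a second role, as an unbiased external validation of the dosing algorithm. The whole method is one clause: "we will repeat the multiple regression analysis in the control sample and compare the coefficients to those in our original equation". It names no equation, outcome visit, way of comparing coefficients or degree of agreement that would count as validation.

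The document prints two equations. The Background section gives the final pilot model, which uses baseline 25(OH)D, baseline 24,25(OH)2D, follow-up cholecalciferol and follow-up 24,25(OH)2D. Vitamin D Preparation and Dosing repeats it: "in our multiple regression analysis to determine characteristics that predict 25(OH)D achieved after supplementation, the following equation had an adjusted R^2 of 0.55". The same section then gives a second equation that uses only baseline 25(OH)D, 24,25(OH)2D and cholecalciferol, and states that "the dosing at both baseline and the 3-month follow-up visit will be determined using this equation". No R-squared, residual SD or other measure of fit is given for this second equation. Both come from pilot work described as a "pilot study of 91 community-dwelling postmenopausal women of European ancestry".

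**The concern.** An algorithm that assigns doses by whether a predicted value lies below 35, from 35 to 50, or above 50 ng/mL is only as good as its individual predictions near those limits. An external validation should therefore show how far the predictions of the equation in use lie from what was observed. The planned step may be aimed at either equation, and it compares coefficients, not predictions.

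If H1a fails, or if target attainment differs by ancestry, the investigators will want to know whether the equation predicted poorly or whether the doses did not move women as expected. H1b compares attainment between ancestry groups, and the exploratory models add "two-way interaction terms between ancestry and each of our primary predictors". Neither scores the fixed equation against observed values. This matters because the pilot women were of European ancestry, while about half of this trial is planned to be of African ancestry.

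**Working it through.** **1. Size of the validation sample.** Sample Size Justification gives 150 evaluable controls. This reproduces. For 40% versus 55%, one-sided alpha 0.05 and power 80%, the uncorrected formula gives 136 per arm. The continuity correction, (136/4) × [1 + sqrt(1 + 4/(136 × 0.15))]^2 = 149.0, rounds up to 150, and 150/0.90 rounds up to 167. So n = 150 is used below, with about 75 per ancestry group if the split stays near equal.

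**2. The two candidate targets.**

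| Term | Follow-up-value model | Baseline-only equation (sets doses) |
|---|---|---|
| Intercept | 8.3 | 18.19385 |
| Baseline 25(OH)D | 1.05 | 0.65967 |
| Baseline 24,25(OH)2D | -7.7 | +1.02393 |
| Cholecalciferol | 0.53 (follow-up) | 0.13564 (baseline) |
| Follow-up 24,25(OH)2D | 4.2 | none |
| Adjusted R-squared | 0.55 | not given |

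The models adjust for different terms, so the change of sign is not in itself an error. It does mean that the result of the comparison depends on which column is the reference.

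**3. Where the predictions lie.** With 24,25(OH)2D equal to d and cholecalciferol zero, the baseline-only equation crosses 35 at (35 - 18.19385 - 1.02393 × d)/0.65967. For d = 0, 2 and 4 (assumed values) this is 25.5, 22.4 and 19.3 ng/mL, all inside the eligible screening range of 10.0-29.9. If baseline 25(OH)D were uniform over that range, its SD would be 19.9/sqrt(12) = 5.74, and its contribution to the SD of predictions 0.65967 × 5.74 = 3.8. An assumed prediction SD of 3-4 and mean of 31-35 is therefore reasonable.

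**4. What identical coefficients would show.** Suppose the refit reproduces the dosing equation exactly. Let predictions be normal with mean m and SD s, and let observed = predicted + normal error with SD r. The probability that both lie on the same side of 35 is:

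| s | r | m = 31 | m = 33 | m = 35 |
|---|---|---|---|---|
| 3 | 6 | 0.741 | 0.674 | 0.648 |
| 3 | 10 | 0.659 | 0.611 | 0.593 |
| 4 | 6 | 0.752 | 0.705 | 0.687 |
| 4 | 10 | 0.671 | 0.634 | 0.621 |

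At m = 35 this reduces to 0.5 + arcsin(rho)/pi with rho = s/sqrt(s^2 + r^2). For s = 3 and r = 6, rho = 0.447 and the result is 0.648. The settings imply R-squared, s^2/(s^2 + r^2), from 9/109 = 0.08 to 16/52 = 0.31. Even if the dosing equation had the 0.55 reported for the other model, rho = sqrt(0.55) = 0.742 and agreement at m = 35 would be 0.5 + 0.836/3.142 = 0.77.

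**5. What a direct check would deliver.** The 95% half-width of mean observed minus predicted is 1.96 × r/sqrt(n):

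| r | n = 150 | n = 75 |
|---|---|---|
| 6 | 0.96 | 1.36 |
| 8 | 1.28 | 1.81 |
| 10 | 1.60 | 2.26 |

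For agreement, 1.96 × sqrt(p(1 - p)/n) with p = 0.6-0.7 gives 0.08-0.07 at n = 150 and 0.11-0.10 at n = 75. For the calibration slope, 1.96 × r/(s × sqrt(n)) gives 0.24-0.53 at n = 150 and 0.34-0.75 at n = 75. Slopes within an ancestry group would thus be descriptive only.

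**The case against.** The sentence concerns the dosing algorithm, and only the baseline-only equation sets doses, so that equation may be the plain referent of the original equation. The Protocol Overview also describes the algorithm in terms of baseline 25(OH)D and 24,25(OH)2D. This reading is fair. It is why the point made here is that the target is ambiguous.

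A reader might infer the opposite: that the follow-up-value model is meant, because the document ties its regression wording and R-squared to that model, and because Aim 2 says "We will expand our predictive model to include baseline serum cholecalciferol and body composition", as though baseline cholecalciferol were not yet included. The document does not establish that either. The baseline-only equation already contains baseline cholecalciferol, although the Background section reports that "virtually all values were zero since the assay is currently not capable of measuring very low concentrations of cholecalciferol". That is a tension between sections, and it does not show which equation the validation sentence means.

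It can also be said that a refit would normally yield R-squared and residual error. In addition, if it used the dosing equation's own predictors, the mean prediction error would equal the covariate means multiplied by the coefficient differences. Both statements are right, so coefficient comparison is not empty. But a refitted model's residual error is not the error of the fixed equation, and cut-point agreement is still not reported.

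Finally, H1a tests the algorithm by randomisation, and the panels will exist whatever the plan says, so the scoring could be done later. This stands and limits the importance of the point. What would be lost is prespecification of the target and the measures.

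**Conclusion.** The point holds as a gap in a secondary validation. The plan names neither the equation nor the visit, and on either reading comparing coefficients does not show how accurate the dosing equation is for individual women. Under the assumptions above, agreement at 35 ng/mL would be only about 59-75% even if the coefficients matched perfectly. Residual SD, prediction mean and SD, and metabolite values are assumptions, because the document gives none for the dosing equation.

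A reader might infer that the dosing equation is never validated. The document does not support that: H1a is a randomised test of the algorithm and is unaffected, and the validation sentence may refer to the dosing equation. A reader might also infer that coefficients will be tested one at a time with low power. The plan states no such procedure, so no conclusion is drawn about its power.

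**What to change.** Replace the clause with a short paragraph that:

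- names the baseline-only equation in Vitamin D Preparation and Dosing, and six-month 25(OH)D, as the validation target;
- applies that equation with fixed coefficients to the controls' baseline values;
- reports mean observed minus predicted with 95% CI, RMSE, out-of-sample R-squared, calibration intercept and slope, and a table of predicted against observed category (<35, 35-50, >50 ng/mL), with mean error and RMSE also by ancestry;
- keeps the refit as a secondary step and says which equation it is compared with;
- states that controls test prediction at 2500 IU only (the pilot used 2300-2500 IU), and that the predicted >50 row will probably be near empty. At a baseline of 29.9 the equation gives 37.9, 40.0 or 42.0 for 24,25(OH)2D of 0, 2 or 4 (assumed) with zero cholecalciferol, so passing 50 would need a cholecalciferol value of about 89, 74 or 59.

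The flow chart already schedules the vitamin D panel at baseline, 3 and 6 months. No visits, samples or participants are added. The change should be made before control-arm outcomes are analysed.

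### Aim 2 is sized on the single-dose control arm and specifies no dose term, so its data cannot support the promised estimate of the dose needed; the analysis population also needs reconciling

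*Combined protocol and SAP*

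**What the plan says.** All references are to the combined protocol and SAP.

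- **Hypotheses and Specific Aims, Aim 2.** H2a, H2b and H2c each pair an association with 25(OH)D after supplementation with a remark that such women need more or less vitamin D. The section closes: "This predictive tool will allow clinical estimation of the dose needed to achieve a target 25(OH)D level".
- **Statistical Methods, Aim 2.** "we will further develop our dosing algorithm by determining if baseline serum cholecalciferol, baseline body composition, and genotypes in the" two named genes are associated with response. No population, visit or dose term is given. The control sample is mentioned only for re-fitting the original equation as an external validation.
- **Statistical Methods, opening paragraph.** Every analysis is to include all randomised women by intention to treat.
- **Sample Size Justification.** The H2a-c regressions are sized "with a total sample size of 150 from the control arm", and with "power of 80% we would be able to detect a factor that accounts for as little as 8% of the variation".
- **Vitamin D Preparation and Dosing.** Controls receive 2500 IU/day throughout. In the algorithm arm, an equation in baseline 25(OH)D, 24,25(OH)₂D and cholecalciferol predicts 25(OH)D, and cut-offs at 35 and 50 ng/mL turn the prediction into 4000, 2500 or 1000 IU. The dose is set again at month 3 from month-3 values.

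**The concern.** To say what dose a woman needs, one must know how far 25(OH)D moves when dose changes, and whether body size, cholecalciferol or genotype alters that movement. A sample on one assigned dose carries no randomised information on either. The earlier data do not fill the gap: the pilot described under Background used 2300-2500 IU/day, and the equation built on it has no dose term.

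The other reading of the plan has its own problem. If all randomised women are analysed without a dose term, the algorithm arm brings in a dose that was set by some of the predictors under study. Baseline cholecalciferol (H2b) is itself in the dosing equation. Body mass and genotype would be affected to the extent that they correlate with the equation's terms.

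So under either reading, Aim 2 as written does not yield an estimate of how dose should change with a woman's characteristics.

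**Working it through.** **1. The plan's own figures.** The 150 per arm comes from H1a: 40% against 55%, 80% power, "a one-sided significance level (α) of 0.05". A two-proportion calculation with continuity correction gives 150 per arm, and 150/0.9 = 166.7, so 167. That reproduces.

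For H2a-c the plan gives 8% at n = 150. The check used the noncentral F test with λ = n·f² and f² = R²/(1 − R²), α 0.05, power 80%:

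| Test | n | f² | Detectable R² |
|---|---|---|---|
| 1 df, two-sided | 150 | 0.0530 | 0.0530/1.0530 = 5.0% |
| 5 df joint | 150 | 0.0889 | 0.0889/1.0889 = 8.2% |
| 1 df, two-sided | 300 | 0.0263 | 0.0263/1.0263 = 2.6% |
| 5 df joint | 300 | 0.0436 | 0.0436/1.0436 = 4.2% |

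The stated 8% is not the 1-df value, at which power would be 94.8%. It is close to a 5-df joint test (power 79.0% at 8%) or to a Bonferroni correction for about 6 to 10 tests (7.6 to 8.4%). The plan does not state the number of predictors, the sidedness or any multiplicity adjustment.

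**2. Dose in the control arm.** Assigned dose is 2500 for every woman, a multiple of the intercept column. A design matrix with intercept, two predictors and dose has rank 3 of 4. No dose coefficient exists, and no dose-by-predictor interaction can be fitted. This needs no assumption.

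**3. What the algorithm arm adds.** Starting dose there is a fixed function of three measured baseline values, and arm is randomised 1:1. Women predicted below 35 ng/mL are thus randomised between 2500 and 4000 IU. Women predicted from 35 to below 50 get 2500 IU in both arms and supply no dose contrast. At the top of the eligible range the prediction is 18.19385 + 0.65967 × 29.9 = 37.9 ng/mL plus the other two terms, so exceeding 50 needs more than 12 ng/mL from those terms. If 24,25(OH)₂D is at most 4 and cholecalciferol at most 10 (assumed), they add at most 1.02393 × 4 + 0.13564 × 10 = 5.5. Starts on 1000 IU should then be absent or rare. Over that assumed range, with uniform baseline 25(OH)D, 36 to 78% of the arm would start on 4000 IU.

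**4. Whether a pooled month-3 model recovers the dose effect.** Assumptions: 150 per arm; true slope 0.60 ng/mL per 100 IU; residual SD 8; baseline 25(OH)D truncated to 10-29.9 (location 20, SD 6); 24,25(OH)₂D about 8% of 25(OH)D with random spread; cholecalciferol exponential with mean 1. About 68% of the algorithm arm then starts on 4000 IU and none on 1000 IU.

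- Pooled slope 0.60, SE 0.07.
- With a curved baseline effect, linear adjustment gives 0.57. Adding the dose category that the equation would assign restores 0.60.
- Other assumptions (slope 5 per 1000 IU, uniform baseline values): pooled slope 4.95, SE 0.73.

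**5. Precision for the allele effect, same assumptions.**

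- Control arm only: SE about 0.70.
- Pooled, common slope: SE about 0.50, a cut of 1 − 0.50/0.70 = 29%, which is simply 1 − 1/√2 from doubling n.
- Pooled with allele-by-dose interaction: SE at 2500 IU of 0.61 to 0.63 in two runs, a cut of 10 to 13%.
- Interaction SE: about 1.06 to 1.08 ng/mL per allele per 1500 IU. For 80% power, two-sided 0.05, the interaction must be about 2.8 × 1.07 = 3.0. That is a third of the assumed dose effect itself over 1500 IU (0.60 × 15 = 9).

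**6. Leaving dose out.** On the same assumed slope, a woman just under the 35 ng/mL cut-off gets 1500 IU more than one just over it, worth about 9 ng/mL, in the direction opposite to her lower prediction. Omitting dose would therefore distort the coefficients of the equation's terms.

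**The case against.** The strongest reply is that the plan is coherent on its own terms. H2a-c test associations, the remarks on dose are interpretation, and associations can be tested at a fixed dose. The control arm matches the pilot dose, stays on one dose for six months, and avoids a dose that depends on the predictors. This stands, and it is why the control-arm analysis should be kept. It does not rescue the statement about the dose needed.

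Several stronger readings are tempting but not supported:

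- *Aim 2 is definitely confined to the control arm.* This rests on the sample-size sentence alone. The Aim 2 methods name no population, and the general rule says all randomised women. What can be documented is a conflict.
- *Half the randomised data go unused.* That could be true of Aim 2 only. The algorithm arm is used in H1a, H1b and the free 25(OH)D analysis.
- *The tool cannot assign a dose.* It can, through the cut-offs at 35 and 50 ng/mL. The limitation is that Aim 2 would not estimate that mapping from data.
- *The 8% is wrong.* With the number of predictors unstated, it cannot be called wrong. The 5.0% used for comparison assumes a 1-df test.
- *Pooling delivers a full dose-response.* It does not, given the narrow contrast and weak interaction check shown above.

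Women may also keep their own supplements, so total intake varies somewhat among controls. That variation is not randomised and is no substitute for an assigned dose contrast.

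**Conclusion.** The point holds in a limited form. The plan gives two incompatible populations for Aim 2 and no dose term under either. In the control arm a dose effect and its modification by predictors are not estimable, and this follows from the design without assumptions. The closing claim of Aim 2 therefore goes beyond what its data can show, while the tests of association at 2500 IU remain valid.

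The gain from using both arms is real but modest. The fall from 5.0% to 2.6% holds only for one factor with a common slope across doses. Once interactions are fitted, the precision gain is about 10 to 13%. The main benefit is that a dose coefficient can be estimated at all, over 2500 to 4000 IU in women predicted below 35 ng/mL. The simulated sizes rest on assumed distributions, slope and residual SD. The primary comparison in Aim 1 is not affected.

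**What to change.** 1. Reconcile the all-randomised rule in Statistical Methods with the sample-size sentence, and state the population, visit and model terms for H2a-c.
2. Keep the control-arm regression as external validation of the original equation and as the fixed-dose, six-month analysis of H2a-c.
3. Add a model of month-3 25(OH)D in all randomised women. Its terms are the three equation terms, the dose category the equation would assign (computable in both arms), the new predictors, ancestry, site, assigned starting dose, and dose-by-predictor interactions. Month 3 is used because the later dose depends on month-3 values.
4. If the added model is not wanted, limit the Aim 2 claim to predicting 25(OH)D on 2500 IU/day.
5. State the number of predictors, the sidedness and any multiplicity adjustment behind the 8%.

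The cost is analysis wording and one further model; visits, samples and doses are unchanged. Three drawbacks should be stated in the plan. The added model says little about 1000 IU. Its interaction check has low power. Month 3 does not match the pilot's 4-6 months, which is a further reason to keep the six-month control-arm fit.
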